9.2. Clinical Laboratory Evaluations

Clinical safety laboratory panels include hematology, serum chemistry, immunoglobulins (IgG, IgA, IgM), urinalysis, and coagulation. See Appendix 12 for a list of the clinical safety laboratory tests within each panel.

All clinical safety laboratory tests will be performed by the central laboratory according to the Schedule of Assessments (Appendix 1). Additional tests may be performed locally at any time during the study as determined necessary by the investigator; these data will be listed only and will not be included in summaries.

For continuous results, mean of the observed result, mean change from baseline (post-baseline visits only), and median change from baseline (post-baseline visits only) will be summarized for each scheduled visit. Standard deviation, median, interquartile range, minimum, and maximum will be presented. Additionally, last post-baseline value as well as maximum and minimum post-baseline values (through last safety follow-up visit and including unscheduled visits) and corresponding changes from baseline will be presented. For clinical laboratory measures that are not normally distributed per the Shapiro-Wilk test, the endpoint will be log-transformed when using MMRM methods or non-parametric test to assess change from baseline.

For qualitative results, the number and proportion of patients in each category will be summarized by scheduled visit.

As applicable, analysis of laboratory data will be based on SI units. For NCI-CTCAE gradable parameters, tables summarizing shift in NCI-CTCAE grades from baseline to each scheduled post-baseline timepoint, to last post-baseline assessment, and to worst post-baseline assessment (scheduled or unscheduled) will be displayed in cross-tabulations. For parameters with toxicity grading in both directions (high and low), shift will be presented separately for high and low.

For non-gradable parameters, tables summarizing shift in normal/abnormal classification from baseline to each scheduled post-baseline timepoint will be displayed in cross-tabulations. For parameters with normal/abnormal classification in both directions (high and low), shift will be presented separately for high and low.

For lab parameters, a graph of mean change from baseline (+/- SD) and/or median change from baseline (IQR) over time will be presented by treatment group.

All lab results will be listed by panel. Local lab results will be clearly identified on the listings.

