Once weekly zetomipzomib dosing elicits anti-inflammatory activity without continuous inhibition of immunoproteasome activity as immunoproteasome activity returns to baseline levels in 3 to 7 days after administration. Thus, weekly administration of zetomipzomib, demonstrates anti-inflammatory effects without altering the overall function of the immune system. There are no observed reductions in circulating leukocytes, normal antibody responses to

vaccination and viral clearance following infection are observed in animal models, and no reduction in immunoglobulins are seen in patients.

Safety of zetomipzomib has also been evaluated in studies of patients with SLE with or without LN, and patients with dermatomyositis (DM) and polymyositis (PM). To date, zetomipzomib has been well tolerated in these studies at weekly doses of 45, 60, and 75 mg. Initial subcutaneous doses of zetomipzomib are occasionally associated with at least 1 of the following signs/symptoms regarded as systemic injection reactions (SIRs): hypotension, tachycardia, nausea, vomiting, dizziness, headache, pyrexia, rigors, and/or chills. The events are associated with an acute phase-like response, including leukocytosis and elevated C-reactive protein, typically begin within 8 to 24 hours after dosing, and usually resolve within 48 hours of dosing. Although the numbers are small, the percentage of patients reporting treatment-emergent adverse events (TEAEs) of the above-mentioned signs/symptoms appears to be lower in patients who received zetomipzomib as step-up doses and/or with pre/post dose prophylaxis, suggesting that these methods are effective at tolerizing patients to higher doses of zetomipzomib. The most common adverse events (AEs), at any dose, were predominantly injection site reactions such as erythema, induration, and tenderness (pain), which were generally mild and transient in nature. Following 4 weeks of treatment, zetomipzomib did not result in persistent laboratory abnormalities as commonly seen with the dual-targeting proteasome inhibitors (eg., thrombocytopenia, anemia, and neutropenia). Overall, subcutaneous administration of zetomipzomib was well tolerated at doses that resulted in potent and selective inhibition of the immunoproteasome.

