## **6.2.1.3.** Mycophenolate Mofetil

Patients will receive background standard of care of "MMF or equivalent," which refers to MMF, MPA, and mycophenolate sodium. MMF 1 g is equivalent to mycophenolate sodium 720 mg.

Oral MMF is a required concomitant medication after randomization, unless the patient is taking equivalent doses of other oral forms, such as MPA and mycophenolate sodium. Patients who are taking other oral forms of mycophenolate may be switched to MMF after randomization at the Investigator's discretion. Patients should be informed of and follow appropriate local practice for this medication, including laboratory monitoring and contraception. MMF will be provided at the sites, or the costs of MMF up to 3 g/day or equivalent will be reimbursed.

Twice daily (BID), 3 times daily (TID) and 4 times daily (QID, if needed due to gastrointestinal AEs) dosing are permitted. The target dose is 2 g/day (e.g., 1 g BID), with doses from 1 g/day to 3 g/day permitted with consultation of the Medical Monitor.

Patients receiving MMF should continue their current dose or, if receiving >2 g/day, will decrease the dose to 2 g/day on Day 1 (Week 1) unless a higher dose (up to 3 g/day) is approved by the Medical Monitor. If >2 g/day is permitted, this dose will not be continued for more than 24 weeks in total nor after Week 25.

For patients who are not currently receiving MMF or equivalent, they will start MMF during the first week (after Week 1 dose of zetomipzomib or placebo) at 1 g/day (0.5 g BID) and increase to 2 g/day (e.g., 1 g BID) during the second week (after Week 2 dose of zetomipzomib or placebo). A complete blood count (CBC) must be performed locally after starting or dose increases. In patients who were not already taking MMF or equivalent at Screening and thus started MMF after randomization, a CBC must additionally be done locally at approximately Weeks 2, 3, and 4 and as per local practice thereafter. After dose increases of MMF or equivalent, CBC must be monitored as per local practice. To aid in distinguishing possible gastrointestinal adverse effects, such as nausea, it is recommended to wait 2 days after the first and second doses of zetomipzomib or placebo, before MMF is started (Day 3) or increased (Day 10), respectively. If a MMF dose of at least 1 g/day is not tolerated, then the patient may be switched to other equivalent forms of mycophenolate at the Investigator's discretion. If a dose of MMF or

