# 7.2.4.6. Clinical Laboratory Tests

Clinical laboratory tests for safety (eg, hematology, serum chemistry, urinalysis, and coagulation) and clinical laboratory tests for efficacy measures such an assessment of immunological variables and biomarkers will be performed at a central laboratory at the visits specified in the Schedule of Assessments (Appendix 3).

A listing of the clinical laboratory tests evaluated for safety is provided in Table 3.

Table 3: Clinical Laboratory Tests for Safety

Hematology	Serum chemistry (non-fasting)	Urinalysis	Coagulation and Other
hemoglobin	creatinine	рН	INR
hematocrit	creatine kinase	glucose	APTT
WBC count (total and	urea (or BUN)	ketones	fibrinogen
differential)	AST	blood	lupus anticoagulant
RBC count	ALT	protein	panel
reticulocyte count	GGT	creatinine	HbA1c
platelet count	alkaline phosphatase	microscopy	
MCV	LDH	leukocyte esterase	
MCH	total bilirubin	nitrite	
MCHC	albumin		
	total protein		
	sodium		
	bicarbonate		
	potassium		
	chloride		
	glucose		

Hematology	Serum chemistry (non-fasting)	Urinalysis	Coagulation and Other
	uric acid		
	total cholesterol		
	LDL cholesterol		
	triglycerides		
	magnesium		
	calcium		
	phosphorus		
	C-reactive protein		

ALT=alanine aminotransferase; APTT=activated partial thromboplastin time; AST=aspartate aminotransferase; BUN=blood urea nitrogen; GGT=gamma-glutamyl transferase; HbA1c=hemoglobin A1c; INR=international normalized ratio; LDH=lactate dehydrogenase; LDL=low-density lipoprotein; MCH=mean cell hemoglobin; MCHC=mean cell hemoglobin concentration; MCV=mean cell volume; RBC=red blood cell; WBC=white blood cell.

Other infectious disease blood tests screening for HBsAg, HBcAb, hepatitis C antibody, and HIV will be performed at the Screening visit only. Positive screens may require additional testing. For those HBcAb-positive patients permitted to enter the study (HBcAb positive, HBsAg negative, HBsAb titer ≥100 IU/L, and negative hepatitis B DNA), additional assessments for hepatitis B DNA should be performed at the visits indicated in the Schedule of Assessments (Appendix 3).

HbA1c, total cholesterol, LDL cholesterol and triglycerides will also be performed for the GTI at the visits indicated in the Schedule of Assessments (Appendix 3).

Unscheduled or additional laboratory samples may be collected and analyzed by local laboratories if immediate results as necessary for management of TEAEs or dosing determination. Urine pregnancy tests will be performed locally.

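### SAP 9.2 lists local laboratory results but does not summarise them, so the worst-grade and minimum/maximum hematology rows can miss early cytopenias seen only on the protocol-required local blood counts

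*SAP*

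**What the plan says.** SAP 9.2 begins from the premise that "All clinical safety laboratory tests will be performed by the central laboratory according to the Schedule of Assessments (Appendix 1"). It then adds "Additional tests may be performed locally at any time during the study as determined necessary by the investigator", and of those results says "these data will be listed only and will not be included in summaries". Local results are to be identified in the listings, so the plan expects them to be in the database.

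The same section sets two extreme-value summaries. Continuous results get "maximum and minimum post-baseline values (through last safety follow-up visit and including unscheduled visits"), with changes from baseline. For CTCAE-gradable parameters, shifts from baseline to each visit, to the last value and "to worst post-baseline assessment (scheduled or unscheduled) will be displayed in cross-tabulations".

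Protocol 6.2.1.3 requires a local CBC after MMF is started or its dose increased. For patients not on MMF or equivalent at Screening, it says that "a CBC must additionally be done locally at approximately Weeks 2, 3, and 4 and as per local practice thereafter". SAP Appendix 1 footnote j, attached to the clinical laboratory row of the schedule, repeats the Week 2 to 4 requirement. Protocol 7.2.4.6 adds a permission: "Unscheduled or additional laboratory samples may be collected and analyzed by local laboratories if immediate results as necessary for management of TEAEs" or for dosing decisions.

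**The concern.** An extreme-value table exists to show the worst result a patient had, whenever it occurred. SAP 9.2 defines these tables to include unscheduled assessments, yet it removes a whole source of results from them without saying how the two rules fit together. It also describes all scheduled testing as central, which its own Appendix 1 contradicts for the early CBCs.

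The required local counts fall in the first month. In that month MMF is started and increased in these patients, and patients assigned to the higher dose level step up at Week 2. Thrombocytopenia and acute renal change are also among the signs by which the protocol identifies suspected thrombotic microangiopathy, an adverse event of special interest. What is at stake is whether the laboratory tables can serve as an objective cross-check on investigator-reported events in that period.

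**Working it through.** The plan states no figure on this point, so the check sets the schedule against the summary rules.

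**1. Central panels.** The clinical laboratory row in SAP Appendix 1 has draws at Screening, Week 1, every 4 weeks from Week 5 to Week 53, at Week 56 and at early termination. Scheduled post-baseline panels: 13 (Weeks 5 to 53) + 1 (Week 56) = 14. None is at Week 2, 3 or 4.

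**2. The gap in days.** Study day = (week − 1) × 7 + 1. Weeks 2, 3, 4 and 5 are Days 8, 15, 22 and 29. With a window of ±2 days, the first central draw after Day 1 is due no earlier than Day 27. Scheduled central panels from Day 2 to Day 26: 0. Required local CBCs in that interval for MMF starters: 3.

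**3. Could the by-visit tables recover them?** The windows are in SAP Section 4, Table 2.

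| Local CBC | Window | Result |
|---|---|---|
| Day 8 | Week 2 (Days 2 to 19) | No panel planned at Week 2, so not flagged for analysis |
| Day 15 | Week 2 (Days 2 to 19) | Same |
| Day 22 | Week 5 (Days 20 to 43) | The scheduled Week 5 draw takes precedence |

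They could not, so the extreme-value rows are the only laboratory summaries in which these counts could appear.

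**4. Does the listing-only rule cover them?** Its sentence literally concerns additional tests that the investigator judges necessary, whereas these CBCs are required. But SAP 9.2 knows only two kinds of test, scheduled central and additional local, and a required local CBC is neither. Listing only is the likely reading, because the section gives local data no other destination. Under that reading, 0 of the 3 CBCs enter the minimum/maximum or worst-grade rows.

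**5. Creatinine.** A CBC does not measure it, and no local creatinine is required. It can be lost only where an unscheduled test was done locally, which Protocol 7.2.4.6 permits but does not require.

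**6. Size.** The documents do not give the share of MMF starters, the frequency of early cytopenia or its duration. As an illustration only, assume that 20% to 60% of patients are MMF starters, that 5% to 10% of those have an early Grade 3 or higher cytopenia, and that 30% to 70% of these resolve before Week 5. With 83 patients per arm:

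- low: 83 × 0.20 × 0.05 × 0.30 = 0.25 patients
- high: 83 × 0.60 × 0.10 × 0.70 = 3.5 patients

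The Safety Population also includes pure Class V patients, up to 83 + 10 = 93 per arm, which gives 0.28 to 3.9. All three shares are assumptions.

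**The case against.** The strongest reply is that the adverse event tables catch what matters. Protocol 9.1.1 makes a clinically significant abnormal laboratory finding an adverse event, whichever laboratory reported it. Such events enter the tables by maximum severity (SAP 9.1.3), the serious event tables (9.1.4), the special-interest tables (9.1.5) and the exposure-adjusted rates (9.1.12). This stands, and it means that a reader should not infer that local results vanish from all safety reporting: the rule governs laboratory summaries. But the route is partial. It depends on a judgment of clinical significance, and Protocol 9.4 keeps non-serious new or worsening SLE manifestations out of the adverse event record. Thrombocytopenia and leukopenia are SLEDAI-2K items (SAP Appendix 7), and inclusion criterion 10 allows for cytopenias attributed to lupus. A non-serious cytopenia ascribed to SLE and seen only locally could be absent from both sets of tables.

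It is also fair to say that event-driven samples are not generally local. Telehealth samples go to the central laboratory (Protocol 7.1.2), and unscheduled samples analysed centrally do count towards the worst value. An abnormality still present at a central draw is captured too.

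Finally, central-only summaries are an openly stated choice that avoids mixing assays, and the documents do not show that local reference ranges are collected across about 214 sites. Adding local counts also gives MMF starters three extra chances at a worst value, and MMF use at Screening is not a stratification factor. These are real costs. But MMF starters are spread over the arms by randomisation, so the extra draws do not in themselves bias the comparison, and a parallel version of the table answers the assay objection.

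**Conclusion.** The inconsistency is real and should be corrected. Followed as written, the worst-grade and minimum/maximum hematology rows can miss an early transient cytopenia in MMF starters. The same rows can miss other abnormalities, including creatinine, where the only measurement was an unscheduled local one. The hematology part rests on reading the required CBCs as listing only, which is likely but not explicit.

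The number of grade shifts lost cannot be computed from the documents; the illustration suggests anything from a fraction of a patient to a few per arm.

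Three stronger inferences are not supported:

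- **Unequal loss between arms.** This is possible, since event-driven tests follow events, but nothing in the documents shows it.
- **A fixed detection rate.** Dividing an assumed duration by the 28-day central interval gives 7/28 = 25%, 10/28 = 36% and 14/28 = 50%. These figures rest on assumed durations and random onset and ignore unscheduled central draws, so they are not loss rates.
- **Expected cytopenia from zetomipzomib.** Protocol 1.2 names thrombocytopenia, anemia and neutropenia as common with dual-targeting proteasome inhibitors, but in a sentence saying that 4 weeks of zetomipzomib did not produce persistent abnormalities of that kind. It gives a reason to look, not evidence of the effect.

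**What to change.** Amend SAP 9.2 before unblinding. The change concerns reporting only and alters no clinical procedure.

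- Correct the statement that all tests are central so that it agrees with Appendix 1 footnote j, and state how the required local CBCs are handled.
- Keep by-visit means, changes and shifts central-only.
- Include local results, converted to SI units and CTCAE-graded, in the shift to worst post-baseline grade and in the minimum/maximum rows, or in a parallel version of both. Do so at least for hemoglobin, platelets, neutrophils and white cells, and for creatinine where a local value exists.
- Footnote, by arm, how many worst values are local.

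The cost is SAP wording, unit conversion and programming on results already planned for listing. Some grades may need local reference ranges; where these are not held, say which parameters are left out. Local and central assays will mix in these rows, which the footnote or the parallel version makes visible.

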9.2.1. Hematology

Hematology results will be summarized, plotted, and listed as applicable per Section 9.2.

9.2.2. Serum Chemistry

Serum chemistry results will be summarized, plotted, and listed as applicable per Section 9.2.

9.2.3. Urinalysis

Urinalysis results will be summarized, plotted, and listed as applicable per Section 9.2.

9.2.4. Coagulation

Coagulation results will be summarized, plotted, and listed as applicable per Section 9.2.

9.2.5. Immunoglobulins (IgG, IgA, IgM)

Immunoglobulin (IgG, IgA, IgM) results will be summarized, plotted, and listed as applicable per Section 9.2.

9.3. Vital Sign Measurements

Vital signs will be taken before blood collection (if applicable at the visit) and prior to zetomipzomib or placebo administration. A second set of vital signs will be obtained on the Day 1 (Week 1) visit 30 minutes (±15 minutes) after zetomipzomib or placebo has been administered.

The following vital sign assessments will be made according to the Schedule of Assessments (Appendix 1):

- Blood pressure (systolic and diastolic in mmHg)
- Pulse rate (beats/min)
- Respiratory rate (breaths/min)
- Body temperature (°C)
- Height (cm; collected at Screening visit only)
- Weight (kg; not collected at telehealth visits)
- BMI (kg/m^2)

Vital signs will be summarized using descriptive statistics by scheduled visit (and time point, if applicable) within each treatment group.

A graph of mean change from baseline (+/- SD) over time will be presented by treatment group for all vital signs.

All vital sign data will be listed.

9.4. Physical Examination

A full physical examination will be performed at Screening only. A symptom-directed brief physical examination will be performed at all other visits. Body systems assessed will include:

- General Appearance
- Head
- Eyes
- Ears
- Nose
- Throat
- Neck
- Dermatological
- Respiratory
- Cardiovascular
- Abdomen
- Extremities
- Neurological
- Musculoskeletal

The number and percentage of patients with the following findings for each body system will be summarized by treatment group:

- Normal
- Abnormal, NCS
- Abnormal, CS
- Not done

All physical examination data will be listed.

9.5. Electrocardiogram

A 12-lead ECG with QTcF interval will be performed at Screening, Week 25 (between 30 minutes to 4 hours post-dose), Week 53 (EOT) and the ETV, if applicable. The ECG will be performed prior to vital sign assessments and following 10 minutes of supine rest.

The following ECG parameters will be summarized by treatment group and visit:

- PR interval (msec)
- RR interval (msec)
- QRS duration (msec)
- QT interval (msec)

- QT interval, categorical (msec)
 - <500
 - >500
- QT interval, categorical change from baseline (msec)
 - <60
 - >60
- QTcF interval (QT interval with Fridericia's correction*; msec)
- QTcF interval, categorical (msec)
 - ≤450
 - >450 ≤480
 - >480
- QTcF interval, categorical change from baseline (msec)
 - ≤30
 - >30 <60
 - >60
- Overall ECG interpretations
 - Normal
 - Abnormal, NCS
 - Abnormal, CS
 - Not done

All ECG data will be listed.

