4. GENERAL STATISTICAL CONSIDERATIONS

This section presents general rules for the derivation and reporting of study data. If a subsequent section related to a specific derivation or analysis differs from this general guidance, the subsequent section takes precedence.

Unless specified otherwise, all study data will be summarized using descriptive statistics. Descriptive statistics for continuous data include number of patients (n), mean, standard deviation (SD), median, quartiles, minimum, and maximum. Categorical data will be described using frequency counts and percentages in each category.

Mean, median, and quartiles will be displayed to one level of precision greater than the data as originally collected. Standard deviation will be displayed to two levels of precision greater than the original data. For the summary statistics of all numerical variables, unless otherwise specified, minimum and maximum will be displayed to the same level of precision as the original data.

When count data are presented, the percentage will be suppressed when the count is zero to draw attention to the non-zero counts. A row denoted "Missing" will be included in count tabulations where specified on the shells to account for missing values. Unless otherwise specified, the denominator for all percentages will be the number of patients in that treatment group within the analysis set of interest. Percentages will be presented to one decimal place except for the display of 100% frequency which will be displayed as 'XX (100)'.

P-values ≥0.001 will be presented to 4 decimal places as "0.xxxx". P-values <0.001 will be presented as "<0.001". P-values >0.999 will be presented as ">0.999". Confidence intervals (CIs) will be displayed to one level of precision greater than the data as collected.

Treatment groups will be labeled as "Zetomipzomib 60 mg", "Zetomipzomib 30 mg", and "Placebo". In general, all tables and figures will be presented by treatment group. All study data will be presented in by-patient data listings sorted by treatment group, patient ID, and assessment date/time.

"No patients qualify for this table" will be presented when there are no data available to report in a given table. A similar note will be presented for empty listings and figures.

For all other parameters, the baseline value will be defined as the last non-missing evaluation prior to the first dose of study treatment (zetomipzomib or placebo), unless otherwise specified.

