Study day will be calculated depending on the assessment date. When an assessment date is before the first dose of study treatment, the study day will be calculated as assessment date – first dose date. If the assessment takes place on or after the first dose of study treatment, the study day will be calculated as assessment date – first dose date ± 1 .

All instances where data may be imputed are detailed in this SAP; no other data imputations are planned. For by-visit summaries, patients will be counted only once for each planned visit. All scheduled and unscheduled assessments including the ETV will be mapped to a scheduled visit by study day according to the analysis visit windows specified in Table 2 (all study assessments except 24-hour urine) or Table 3 (24-hour urine only) below. The assessment used for the by-visit analysis will be selected as follows:

- If there is a corresponding scheduled visit within the analysis visit window, then data
 from the scheduled visit will be used for analysis. In the event of multiple
 corresponding scheduled visits, the visit closest to the scheduled day will be used. In
 the event of a tie, data from the earlier visit will be used.
- If there is no scheduled visit within the analysis visit window, then data from the visit
 closest to the scheduled day will be used for analysis. In the event of a tie, data from
 the earlier visit will be used.

If an assessment falls into an analysis visit window for a visit at which it was not planned to be collected per the protocol (see Appendix 1, Schedule of Assessments), the assessment will not be flagged for use in the by-visit analysis.

All assessments (scheduled, unscheduled, and ETV) will be included in the data listings.

Table 2: Analysis Visit Windows – All Study Assessments Except 24-hour Urine Collection

Visit	Target Day	Analysis Visit Window (Study Days)	Analysis Visit Name
Screening	-35 to -1	≤1	Baseline
Visit 1 / Week 1 (Day 1)	1		
Visit 2 / Week 2	8	2 to 19	Week 2
Visit 3 / Week 5	29	20 to 43	Week 5
Visit 4 / Week 9	57	44 to 71	Week 9
Visit 5 / Week 13	85	72 to 99	Week 13
Visit 6 / Week 17	113	100 to 127	Week 17
Visit 7 / Week 21	141	128 to 155	Week 21
Visit 8 / Week 25	169	156 to 183	Week 25
Visit 9 / Week 29	197	184 to 211	Week 29
Visit 10 / Week 33	225	212 to 239	Week 33
Visit 11 / Week 37	253	240 to 267	Week 37
Visit 12 / Week 41	281	268 to 295	Week 41

Visit	Target Day	Analysis Visit Window (Study Days)	Analysis Visit Name

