Visit 13 / Week 45	309	296 to 323	Week 45
Visit 14 / Week 49	337	324 to 351	Week 49
Visit 15 / Week 53 (EOT)	365	352 to 379	Week 53
Visit 16 / Week 56 (EOS)	393	380 to 395	Week 56

EOS=End of Study; EOT=End of Treatment. Patients are not dosed at Week 53.

Table 3: Analysis Visit Windows – 24-hour Urine Collection Only

Visit	Target Day	Analysis Visit Window (Study Days)	Analysis Visit Name
Screening	-35 to -1	≤1	Baseline
Visit 5 / Week 13	85	72 to 113	Week 13
Visit 8 / Week 25	169	156 to 197	Week 25
Visit 11 / Week 37 ^a	253	240 to 281	Week 37
Visit 15 / Week 53 (EOT)	365	352 to 379	Week 53
Visit 16 / Week 56 (EOS)	393	380 to 421	Week 56

EOS=End of Study; EOT=End of Treatment. Patients are not dosed at Week 53.

All statistical tests will be 2-sided, unless otherwise specified. No statistical comparisons will be performed between the two zetomipzomib dose groups.

All statistical analyses detailed in this SAP will be conducted using SAS® Version 9.4 or higher.

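### Optional ECGs, and on the stronger reading early-termination ECGs, dated outside Days 156-183 and 352-379 enter no between-group ECG table

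*SAP*

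**What the plan says.** SAP 9.5 and Protocol 7.2.4.4 plan ECGs at Screening, Week 25, Week 53 and the ETV. The protocol also allows optional ECGs at other visits at the investigator's discretion. For analysis, SAP 9.5 states "The following ECG parameters will be summarized by treatment group and visit", and otherwise that all ECG data are listed. It specifies no worst-value, last-value or any-post-baseline summary.

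SAP 4 sets the general rules for by-visit tables:

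- Mapping: "All scheduled and unscheduled assessments including the ETV will be mapped to a scheduled visit by study day". The windows are in Table 2, which has no ETV row.
- Choice within a window: "If there is a corresponding scheduled visit within the analysis visit window, then data" from that visit are used. Other assessments are used only when the window holds no scheduled visit.
- Unplanned assessments: where an assessment falls in the window of a visit at which it was not planned, "the assessment will not be flagged for use in the by-visit analysis".
- Precedence: where a later section "differs from this general guidance, the subsequent section takes precedence".

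Laboratory data are treated differently. SAP 9.2 includes a shift from baseline "to worst post-baseline assessment (scheduled or unscheduled) will be displayed in cross-tabulations".

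**The concern.** ECGs are planned at few visits, and the rule in SAP 4 for unplanned assessments removes whatever falls between them. The recordings removed come from patients who leave the study early and from ECGs that an investigator chose to obtain. It is reasonable to suppose that some of the latter follow a clinical concern.

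At stake is whether the comparison of QTcF categories between arms uses all the ECGs collected. By default SAP 4 takes percentages over all patients in the treatment group within the analysis set. A patient whose only post-baseline ECG is not tabulated would then count in the denominator but in no QTcF category, unless the table shells handle this another way.

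**Working it through.** This is a check of rules, and the plan gives no figure to reproduce. The inputs are the windows in SAP Table 2, the ECG row of SAP Appendix 1, and the selection rules in SAP 4.

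**Step 1: which study days count for ECGs.** A post-baseline ECG is tabulated only if its day maps to a visit with a planned ECG.

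| ECG on study day | Maps to | ECG planned there? | In the by-visit table? |
|---|---|---|---|
| 100 | Week 17 | No | No |
| 155 | Week 21 | No | No |
| 156 and 183 | Week 25 | Yes | Yes, unless displaced |
| 184 | Week 29 | No | No |
| 351 | Week 49 | No | No |
| 352 and 379 | Week 53 | Yes | Yes, unless displaced |
| 380 | Week 56 | No | No |

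An unscheduled ECG inside a window is displaced when that window already holds the scheduled-visit ECG.

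**Step 2: effect per patient, with ETV ECGs mapped by study day.**

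- ETV ECG before Day 156: 0 of 1 planned post-baseline ECG is tabulated.
- Week 25 ECG, then an ETV ECG on Days 184-351: 1 of 2 is tabulated.
- Drug stopped but patient stays in the study: the planned ECGs remain and nothing is lost.

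**Step 3: comparison with vital signs.** SAP 9.3 says "Vital signs will be summarized using descriptive statistics by scheduled visit" and has no worst-value row either. But vital signs are planned at every visit, and their windows (2-19, 20-43, 44-71, and so on to 352-379 and 380-395) run without a gap from Day 2 to Day 395. An ETV vital sign in that span therefore always maps to a visit where it was planned. Displacement within a window affects vital signs too; the gaps between windows affect ECGs.

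**Step 4: whether drug exposure justifies leaving these ECGs out.** Protocol 6.2.5 gives a half-life under 5 hours, and Protocol 8.1.2 encourages withdrawing patients to complete the ETV within 14 days, so an ETV ECG may be taken with little drug present. The Week 53 ECG has the same limit and is tabulated. Weekly dose k falls on Day 7(k - 1) + 1, so dose 52 falls on Day 7 × 51 + 1 = 358. The Week 53 target is Day 365, and 365 - 358 = 7 days = 168 hours. At 5 hours per half-life that is 168 / 5 = 33.6 half-lives. The note to Table 2 agrees: "Patients are not dosed at Week 53".

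**Step 5: the top QTcF band, a separate and smaller matter.** SAP 9.5 stops at >480 ms for QTcF, while uncorrected QT has a cut at 500 ms. Assume that baseline B is the Screening ECG, so B ≤ 480 under exclusion criterion 11. A value V > 500 with a rise V - B ≤ 30 requires B ≥ V - 30 > 470, and V ≤ 480 + 30 = 510. Only baselines above 470 and up to 480 ms with values above 500 and up to 510 ms stay in the ≤30 change category; an example is 475 to 502, a rise of 27. Above 510 ms the rise always exceeds 30 ms, so the change table already separates those values from a small drift such as 478 to 484.

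**The case against.** The strongest reply concerns the ETV. SAP 9.5 names it as one of the ECG occasions and then summarizes by visit, so a local reading is that the ETV is one of those visits, and the precedence clause lets a later section override SAP 4. SAP 9.5 does not spell out Week 25 or Week 53 rows either, and the table shells, which could settle the matter, are not part of the documents. This stands in part. A reader might infer that every out-of-window ETV ECG is certain to be left out; the documents do not go that far. Exclusion is nevertheless the stronger reading, because SAP 4 sends ETV data through the study-day windows by name and SAP 9.5 states no other mapping. For optional ECGs there is no such doubt.

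Second, the plan does not depart from the protocol. Protocol 10.7 asks for ECG summaries by time point and reserves shift tables for laboratory tests. That is correct, so the point is an improvement and not a protocol inconsistency.

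Third, other routes exist. All ECGs are listed. A medically significant change from Screening is recorded as an AE and can reach the AE tables, including those for TEAEs leading to discontinuation. The IDMC may request further analyses (SAP 12). It would therefore be wrong to infer that the data are lost or that a cardiac signal would go unseen. But the AE route depends on investigator judgment, and none of these routes puts the ECG values into an ECG table.

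Fourth, the importance may be slight. Protocol 1.2 reports no significant safety pharmacology signals, and no cardiac event is an AESI. This supports a low priority.

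Fifth, a worst-value row has a weakness of its own. It pools clinically triggered ECGs with routine ones, and patients with more ECGs have more chances of an extreme value, so arms could differ through ascertainment alone. This stands and belongs in a footnote.

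**Conclusion.** The point holds as a minor gap in descriptive safety reporting. It touches no efficacy result. For optional ECGs it follows directly from the rules in SAP 4. For ETV ECGs it rests on SAP 4's mapping applying because SAP 9.5 states no alternative.

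The size in patients is unknown, because the documents give no early-termination rate and no optional-ECG rate. The two ECG windows cover 28 + 28 = 56 of the 394 days from Day 2 to Day 395 (14.2%). A reader might infer that a similarly small share of ECGs is tabulated. That does not follow: this is a share of calendar days, and planned ECGs are scheduled to fall inside the windows.

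The missing QTcF band above 500 ms is not a cause of the gap and matters less. Given a Screening baseline of at most 480 ms, the change categories already separate any value above 510 ms.

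**What to change.** In SAP 9.5, add a worst post-baseline summary by treatment group, drawing on scheduled, unscheduled and ETV ECGs, for QTcF category, QTcF change category and overall ECG interpretation. This follows what SAP 9.2 does for laboratory data. Keep the by-visit tables as they are.

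Footnote the new summary to say that it pools ECGs not timed to dose, since only Week 25 has a required post-dose time, and that it includes clinically triggered ECGs, so the number of ECGs per patient may differ between arms.

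As an optional small addition, split the top QTcF band into >480-500 ms and >500 ms.

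The cost is a few lines of SAP text and one table block from data already collected and listed. No patient needs another ECG. The drawback is the mixed timing and uneven ascertainment that the footnote discloses.
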